9.4 Disposition of Subjects

A subject disposition summary presented by treatment group and overall will be provided. The categories will include all subjects who were randomized, subjects who were not treated, subjects who discontinued from the study categorized by reason, and subjects who completed the study. Post-randomization discontinuation reasons include pretreatment event or adverse event, major protocol deviations, lost to follow-up, lack of efficacy, voluntary withdrawal, study termination, pregnancy, and other. A listing will be presented to describe study treatment, date of first dose, date of last dose, date of completion or early withdrawal, and the reason for early discontinuation for each subject.

A summary of screening failures and listings of inclusion/exclusion criteria responses for subjects with violations will also be provided.

9.5 Demographic and Baseline Characteristics

In countries that do not allow collection of date of birth, a subject's age will be collected at each post-Baseline Study Visit, Unscheduled Visit (as needed), and at the End of Study / Early Withdrawal Visit.

Demographic and baseline characteristics including date of birth or age, gender, Hispanic/Latino ethnicity, race as identified by the subject, non-Hispanic/Latino Caucasian determination, years of education, primary language, ability to communicate in primary language, bilingualism, years lived in the country/region, occupation, smoking status, drinking habit of the subject at Screening Visit, height, weight, body mass index (BMI), family history of dementia and related conditions, APOE genotype, TOMM40 genotype, risk status as identified by the biomarker risk algorithm, diabetic status, and baseline statin use will be listed and summarized for each treatment group and overall. The demographic and baseline characteristics summary will be based on all randomized subjects.

Baseline values for selected efficacy parameters (cognitive battery composite score, ADCS ADL-PI) will also be presented for each treatment group and overall based on all randomized subjects.

Height and weight values will be presented in metric units (cm and kg respectively). BMI is calculated as $[\text{weight (kg)}/\text{height (m)}^2]$, using the weight and height collected Visit 2 (Baseline).

Race is classified into White, Black or African American, Asian, American Indian or Alaska Native, Native Hawaiian or Other Pacific Islander. In addition, ethnicity (Hispanic or Latino) is also captured.

For continuous variables, the number of non-missing values and the mean, median, SD, minimum and maximum based on the raw scores uncorrected for demographic modifiers (ie, age, gender, education) will be tabulated by treatment group and overall. For the categorical variables, the count and percentages of each possible value will be tabulated by treatment group and overall.

All individual demographic and baseline data will be listed by treatment, study center and subject number.

9.6 Medical History and Concurrent Medical Conditions

Medical history refers to significant conditions/diseases that stopped at or prior to Screening (time of informed consent). Concurrent medical conditions are those significant ongoing conditions/diseases present at Screening (time of informed consent). Family history of dementia and related conditions will be collected at the first 6 month visit and at the End of Study/Early Withdrawal visit.

Medical history and concurrent medical conditions will be coded using the Medical Dictionary for Regulatory Activities (MedDRA) latest version and will be summarized by treatment group and overall using System Organ Class (SOC) and MedDRA preferred term. The table will include number and percentages of subjects and will be sorted in alphabetical order by system

organ class and sorted by decreasing frequency order by preferred term. A subject will only be counted once within a particular class even if he/she has multiple conditions/symptoms. Summaries will be based on all randomized subjects.

All medical history and concurrent medical condition data will be listed by treatment, study center and subject number. The listing will contain subject identifier, whether there was any significant medical history or concurrent condition, and include system organ class, preferred term and details of the medical history or condition.

9.7 Medication History and Concomitant Medications

The medication history and concomitant medications are defined as follows:

- Medication history refers to the medication that the study subjects stopped taking within 3 months prior to the Screening Visit (ie, stop date < first screening visit date).
- Concomitant medication is defined as medication that the study subjects continued taking or took from Screening through end of study:
 - Concomitant medication that started and stopped prior to baseline (ie, stop date \geq first screening visit date, and stop date < first dose date).
 - Concomitant medication that started prior to and was ongoing at baseline (ie, start date < first dose date, and stop date > first dose date).
 - Concomitant medication that started after baseline but before or at last dose (ie, start date \geq first dose date, and start date \leq last dose date).
 - Concomitant medication taken during the study (ie, start date \leq last dose date, and stop date \geq first dose date).
 - If start date and stop date are missing, medication will be assumed to occur both prior and concomitantly.

Medication history and concomitant medications will be coded using the latest version of the World Health Organization (WHO) Drug Dictionary and summarized by giving the number and percentage of subjects by preferred term within each therapeutic class, with therapeutic class and medications in each class sorted in order of decreasing frequency. The number of subjects with medications in each reported therapeutic class will also be presented. If a subject reports taking 2 drugs belonging to the same class, he/she will only be counted once within that class. Summaries of medication history and concomitant medication will be based on all randomized subjects.

All prior and concomitant medications will be listed by treatment, study center and subject number. The listings will contain subject identifier, WHO Drug preferred term and reported term, dose, unit, frequency, route, start date, end date, whether the medication was ongoing, whether the medication as given to treat a pretreatment event/adverse event, and reason for use.

9.8 Study Drug Exposure and Compliance

The summary of study drug exposure and compliance will be based on the safety analysis set.

Duration of exposure to double-blind study medication is defined as (date of last dose – date of first dose +1).

Treatment duration will be summarized by duration category in months and the number of subjects in each duration category by treatment group.

- <6 months (1 to 161 days).
- 6 to <12 months (162 to 344 days).
- 12 to <18 months (345 to 526 days).
- 18 to <24 months (527 to 709 days).
- 24 to <30 months (710 to 892 days).
- 30 to <36 months (893 to 1074 days).
- 36 to <42 months (1075 to 1257 days).
- 42 to <48 months (1258 to 1440 days).
- 48 to <54 months (1441 to 1622 days).
- 54 to <60 months (1623 to 1805 days).
- 60 to <66 months (1806 to 1987 days).
- 66 months \geq 1988 days.

Treatment duration (months) will also be summarized using descriptive statistics (n, mean, SD, median, minimum, and maximum).

Percent of study drug compliance is defined as $\{(\text{number of tablets dispensed} - \text{number of tablets returned}) / (\text{date of last dose} - \text{date of first dose} + 1)\} \times 100\%$. If a value for the number of returned tablets is missing or the return date is missing, then 100% compliance will be assigned for each day up to the number of tablets dispensed, up to the date of return, or up to the date of the last visit, whichever is earliest.

For each treatment group, study medication compliance will be summarized by compliance category (<80%, 80 to 120%, and >120%) and the number of subjects in each compliance category. Study medication compliance will also be summarized as a continuous variable using descriptive statistics (n, mean, SD, median, minimum, and maximum) for each treatment group.

All study drug administration and accountability data will be listed by treatment, study site, and subject number. The following variables will be listed: subject identifier, visit, first and last dose dates, medication identification number, drug dispensed and drug returned dates, number of tablets dispensed and returned, and percent compliance.

9.9 Efficacy Analyses

Except as otherwise noted, the analyses and summaries will be based on the FAS.

All primary and key secondary efficacy analyses and summaries will be presented separately for the following groups of subjects:

- Non-Hispanic/Latino Caucasian subjects.
- Hispanic/Latino and/or non-Caucasian subjects.
- All subjects.

All primary, secondary, additional, and other outcomes variables listed below will be presented by treatment group using descriptive statistics by visit (including change-from-baseline for continuous variables) and presented in efficacy listings.

9.9.1 Overview of Primary, Secondary, and Additional Variables

The primary, secondary and additional variables for this study are presented in [Table 9.b](#). While most of the variables in the table are technically discrete, the variable type column indicates how the variables will be considered for purposes of analysis.

Table 9.b Primary, Secondary and Additional Variables

Parameter	Description	Range	Variable Type
MCI_TIME	Time to event of MCI due to AD	N/A	Time-to-event
MMSE	Total of all items correct	0-32	Continuous
MMSE _i	MMSE single item i	0-5	Categorical
BVMT_T1	# of elements recalled, Trial 1 (0-12 possible)	0-12	Continuous
BVMT_T2	# of elements recalled, Trial 2 (0-12 possible)	0-12	Continuous
BVMT_T3	# of elements recalled, Trial 3 (0-12 possible)	0-12	Continuous
BVMT_TOT	Total # of elements recalled, Trials 1-3	0-36	Continuous
BVMT_DEL	Total # of elements recalled after a delay (25-minute delay)	0-12	Continuous
BVMT_HIT	Total # of target elements correctly recognized	0-6	Continuous
BVMT_FP	Total # of foils incorrectly endorsed	0-6	Continuous
BVMTDISC	Total target elements correctly recognized relative to Total false positives	-6 to 6	Continuous
BVMTCOPY	Total # of elements copied correctly	0-12	Continuous
DIGIT_F	Total items correct, Digit Span Forward	0-16	Continuous
DIGIT_B	Total items correct, Digit Span Backward	0-14	Continuous
DIGITOT	Total Forward + Back	0-30	Continuous
TRAILSAS	# of seconds to complete all items, Trails A	0-300	Continuous
TRILSAE	Errors (number of errors committed during the test)	0-5	Continuous
TRAILSBS	# of seconds to complete all items, Trails B	0-300	Continuous
TRILSBE	Errors (number of errors committed during the test)	0-15	Continuous
MINT	Total correct, MiNT	0-32	Continuous
SEMFLU	Number of exemplars generated in 1 minute (up to max=100)	0-100	Continuous
LEXFLU	Number of exemplars generated total for F, A, and S (up to max 267)	0-267	Continuous
LEX_F	Number of exemplars generated in 1 minute (up to max=89)	0-89	Continuous
LEX_A	Number of exemplars generated in 1 minute (up to max=89)	0-89	Continuous
LEX_S	Number of exemplars generated in 1 minute (up to max=89)	0-89	Continuous
CLOCK	Number of elements correct (eg, clock face, hands, number placement), Clock Drawing Test	0-10	Continuous
CVLT_T1	# of words (out of 16), recalled 1st trial	0-16	Continuous
CVLT_T2	# of words (out of 16), recalled 2nd trial	0-16	Continuous
CVLT_T3	# of words (out of 16), recalled 3rd trial	0-16	Continuous
CVLT_T4	# of words (out of 16), recalled 4th trial	0-16	Continuous
CVLT_T5	# of words (out of 16), recalled 5th trial	0-16	Continuous
CVLT_TOT	# of words recalled (16/trial), trials 1-5	0-80	Continuous

Table 9.b Primary, Secondary and Additional Variables (continued)

Parameter	Description	Range	Variable Type
CVLT_TB	# of words (out of 16), recalled, intrusion trial B	0-16	Continuous
CVLTSDEL	# of words (out of 16), recalled, short delay	0-16	Continuous
CVLTLDEL	# of words (out of 16), recalled, long (20 min) delay	0-16	Continuous
CVLTINTR	False positive, words recalled	0-50	Continuous
CVLT_REP	Total words repeated	0-28	Continuous
CVLTHITS	Total target words correctly recognized from recognition list	0-16	Continuous
CVLT_FP	Total foil words incorrectly recognized from recognition list	0-32	Continuous
OVERALL	Composite Score (mean of cognitive battery domain scores)	N/A	Continuous
EPISODIC	Mean of cognitive battery Memory domain scores	N/A	Continuous
EXECUTIV	Mean of cognitive battery Executive Function domain scores	N/A	Continuous
LANGUAGE	Mean of cognitive battery Language domain scores	N/A	Continuous
ATTENTN	Mean of cognitive battery Attention domain scores	N/A	Continuous
GDSSC	GDS Short-Form total score	0-15	Continuous
GDS _i	GDS single item i	0-1	Binary
ADCSTOT	ADCS MCFSI total score	0-14	Continuous
ADCS _i	ADCS MCFSI single item i	N/A	Categorical
EQ5DINDX	EQ-5D index utility score	0-1	Continuous
EQ5D_VAS	EQ-5D VAS score	0-100	Continuous
EQ5D _i	EQ-5D single item i	1-3	Categorical
SF36_PCS	SF-36 Physical Component Summary score	0-100	Continuous
SF36_PCT	SF-36 Physical Component Summary T score	N/A	Continuous
SF36_PCR	SF-36 Physical Component Summary Reliability Consistency Index score	0-100	Continuous
SF36_MCS	SF-36 Mental Component Summary score	0-100	Continuous
SF36_MCT	SF-36 Mental Component Summary T score	N/A	Continuous
SF36_MCR	SF-36 Mental Component Summary Reliability Consistency Index score	0-100	Continuous
SF36_V	SF-36 Vitality domain T score	0-100	Continuous
SF36_P	SF-36 Physical Functioning domain T score	0-100	Continuous
SF36_B	SF-36 Bodily Pain domain T score	0-100	Continuous
SF36_G	SF-36 General Health Perceptions domain T score	0-100	Continuous
SF36_PRF	SF-36 Physical Role Functioning domain T score	0-100	Continuous
SF36_E	SF-36 Emotional Role Functioning domain T score	0-100	Continuous
SF36_S	SF-36 Social Role Functioning domain T score	0-100	Continuous
SF36_M	SF-36 Mental Health domain T score	0-100	Continuous
SF36 _i	SF-36 single item i	1-5	Categorical
IQTOT	IQCODE overall mean score	1-5	Continuous
IQ _i	IQCODE single item i	1-5	Categorical
ADLTOT	ADCS ADL-PI ADL total score	0-45	Continuous
PHYTOT	ADCS ADL-PI Physical Function total score	0-5	Continuous

Table 9.b Primary, Secondary and Additional Variables (continued)

Parameter	Description	Range	Variable Type
ADLQ _i	ADCS ADL single item i	0-3	Categorical
NPIQ_SEV	NPI-Q Total Severity score	0-36	Continuous
NPIQ_CD	NPI-Q Total Caregiver Distress score	0-60	Continuous
NPIQ _i	NPI-Q single item i	0-5	Categorical
CGIC_TOT	ADCS-CGIC-MCI total score	1-7	Categorical
CGIC_COG	ADCS-CGIC-MCI cognition score	1-7	Categorical
CGIC_BHV	ADCS-CGIC-MCI behavior score	1-7	Categorical
CGICFUNC	ADCS-CGIC-MCI functional abilities score	1-7	Categorical
CDR01GS	CDR Global Score	0-3	Continuous
CDR01SB	CDR Sum of Boxes	0-18	Continuous
CDR0102	CDR orientation domain score	0-3	Continuous
CDR0101	CDR memory domain score	0-3	Continuous
CDR0103	CDR judgment and problem-solving domain score	0-3	Continuous
CDR0105	CDR home and hobbies domain	0-3	Continuous
CDR0104	CDR community affairs domain score	0-3	Continuous
CDR0106	CDR personal care domain score	0-3	Continuous
C-SSRS _i	C-SSRS single item i	N/A	Categorical
LHIP_ATR	Left Hippocampal Atrophy	N/A	Continuous
RHIP_ATR	Right Hippocampal Atrophy	N/A	Continuous
WHLB_ATR	Whole Brain Atrophy	N/A	Continuous
VNTENLRG	Ventricle Enlargement	N/A	Continuous

9.9.2 Task Completion, Irregular Procedure, and Missing Items on Rating Scales

The rules for handling missing items from each of the scales are designed so that as much data as possible can be used in the analyses, yet with reliable information, when calculating total scores.

Missing data may occur in the course of the study or may be due to drop-out. With regard to neuropsychological data collection within the study, missing data can occur under several scenarios. In an interview setting administration of some portions of the test battery may be precluded by tester error or factors attributable to the patient (illness, refusal, or other problems). Neuropsychological technicians will be trained to avoid missing data whenever possible. In the event that an item or a test is missing, technicians will be trained to record the reason for missing data. When tests are scored, the reason for missing data will be coded in a uniform, standardized manner across sites.

For some reasons, subjects may not complete the tasks / tests as requested, or subjects used irregular procedure and/or questionable effort. In such cases, the data may be considered unreliable and/or invalid. For baseline and follow-up assessments, the scoring of the following cognitive test instruments, including the assignment of missing value codes, will rely on the NeuroCog Trials expert judgment, and will be clearly indicated in the dataset: MMSE, CVLT-II, BVMT-R, Digit Span tests, Trail Making Tests, MiNT, Semantic and Lexical Fluency tests, and Clock Drawing Test.

The criteria for triggering possible cases for adjudication are provided in the appendix of the CIAC Charter. If values for a particular test are: ‘999’ (not administered due to Cognitive Impairment) or ‘992’ (Refusal), then the test is considered to be failed. This failure will be treated in the same manner as any other 'failed test' in regards to the triggering algorithm. If values for a particular test are: ‘991’ (is missing due to physical/sensory reason) or ‘994’ (‘other’ reason), then the test is treated as missing and as a non-failure.

The following tests which are collected at an item level in the eCRF will be prorated whenever a sufficient percentage of data is non-missing: GDS Short-Form total score, ADCS MCFSI total score, IQCODE Overall mean score, ADCS ADL-PI ADL total score, ADCS ADL-PI Physical Function total score, NPI-Q Total Severity score, and NPI-Q Total Caregiver Distress score.

The general rule when individual items are missing from the multiple-item assessments specified in [Table 9.c](#) below is as follows: The total score will be calculated using a SAS function ROUND, as ROUND[(sum of nonmissing items)×(total number of items)/(number of nonmissing items)]. (The IQCODE Overall mean score is a mean of the item-level values and so will remain unchanged when proration is valid and will be set to missing when prorating is not valid.) If more than 20% of the items are missing, the total score will be set to missing. The implications of this rule are indicated in [Table 9.c](#) for each rating scale. The resulting calculated total scores will be used in all analyses.

Table 9.c Number of Missing Items on Scales with a Missing Value for Total Score

Parameter	Number of Missing Items
GDS Short-Form total score	≥4
ADCS MCFSI total score	≥3
IQCODE Overall mean score	≥6
ADCS ADL-PI ADL total score	≥4
ADCS ADL-PI Physical Function total score	≥2
NPI-Q Total Severity score	≥3
NPI-Q Total Caregiver Distress score	≥3

9.9.3 Analysis of Primary Variable

There are 2 independent null hypotheses in this protocol: (1) assumes that there is no difference in conversion rate between the placebo-treated high-risk and low-risk groups as defined by the prognostic biomarker risk algorithm and (2) assumes that there is no difference in conversion rate between the high-risk active- and placebo-treated subjects. The alternate hypotheses are: (1) there is a difference between the high- and low-risk groups treated with placebo, and (2) there is a difference between placebo and active treatment in the high-risk group.

A futility analysis will be conducted for this study (see Section [9.15](#)).

9.9.3.1 Primary biomarker risk assignment algorithm analysis

In order to test the first hypothesis, a test from a Cox proportional hazards survival model will be used to compare data from non-Hispanic/Latino Caucasian subjects in the (placebo-treated) low-risk group (ie, the combined placebo groups) with data from non-Hispanic/Latino Caucasian subjects in the placebo-treated subjects in the high-risk group. The event in this analysis will be an adjudicated event of MCI due to AD (see Section 9.9.4 below). If this test is significant at the 0.01 level, it can be concluded that the diagnostic prognostic test has differentiated between subjects at low and high risk of being diagnosed with MCI due to AD within 5 years of taking the test.

An exact partial likelihood function will be constructed to fit the Cox proportional hazards (CPH) model to accommodate events with the same times to the event. The robust sandwich estimate for the covariance matrix from the CPH model will be used. The analysis of the primary biomarker comparison will be conducted using the FAS and a CPH model of MCI due to AD events with a factor for biomarker risk assignment and including center, gender, and education as covariates. (Except as otherwise noted, education will be treated as a continuous variable and measured in years for purposes of statistical modeling.)

Parameter estimates, 2-sided 99% CIs, and appropriate p-values for the hazard ratios obtained from the CPH model will be computed to test the null hypothesis of equality of the hazard functions between high-risk placebo and low-risk placebo.

Assessment of the proportional hazards assumption for risk assignment category will be assessed. Plots of Schoenfeld residuals obtained from the CPH models that fit the primary MCI-to-AD endpoint versus ordered time of events along with a smoothing spline will be used to evaluate the proportional hazards assumption for risk assignment category. Systematic departures from a horizontal line are indicative of meaningfully non-proportional hazards. Diagnostic checks will be presented in CSR Appendix 16.1.9.

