 - Approximately 314 subjects in the low-risk group: All subjects stratified to the low-risk stratum will also be randomized to maintain the stratification blind, but all subjects in this stratum will receive placebo.
- Non-Caucasian subjects and Hispanic/Latino Caucasian subjects. Subjects will be allocated to risk strata using the same algorithm as for the non-Hispanic/Latino Caucasian subjects.

Since all subjects screened at the time of Amendment 5 will be allowed to randomize if they continue to meet all eligibility criteria, it is estimated that approximately 3,500 will be randomized with the following groups:

- Non-Hispanic/Latino Caucasian subjects. Estimated 3,330 subjects further divided into:
 - Approximately 2,940 subjects in the high-risk group (pioglitazone, n=1,470; placebo, n=1,470).
 - Approximately 394 subjects in the low-risk group: All subjects stratified to the low-risk stratum will also be randomized to maintain the stratification blind, but all subjects in this stratum will receive placebo.
- Non-Caucasian subjects and Hispanic/Latino Caucasian subjects. Subjects will be allocated to risk strata using the same algorithm as for the non-Hispanic/Latino Caucasian subjects (n=167).

Because the data used to develop the biomarker risk algorithm was collected in non-Hispanic/Latino Caucasian subjects only, biomarker qualification will be based upon non-Hispanic/Latino Caucasian subjects in the placebo arm of the high-risk stratum compared to data from non-Hispanic/Latino Caucasian subjects in the low-risk stratum. Likewise, the primary analyses to evaluate the effects of pioglitazone versus placebo will be within the non-Hispanic/Latino Caucasian high-risk sub-group. Data from non-Caucasian and Hispanic/Latino Caucasian subjects are expected to be limited and will be analyzed as exploratory data to

CCI

An interactive response system will be used for central randomization. Stratification status and treatment assignment of all study participants will be double-blind.

Subjects in the high-risk stratum will be randomized to pioglitazone and placebo in a 1:1 ratio. Subjects in the low-risk stratum will be randomized only to placebo.

Subjects will be instructed to take the first dose of study medication in the morning on the day following the randomization visit. It is recommended that the site may confirm first dose has occurred through a phone call.

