In addition to the primary analysis population, it is anticipated that approximately 5% as many subjects will be Hispanic/Latino and/or non-Caucasian. Additional analyses for Hispanic/Latino and/or non-Caucasian subjects and for all subjects will be done to support the results of the primary analysis. These analyses will be the same as those conducted for the primary subgroup of the Caucasian subjects in order to evaluate the biomarker effectiveness within this extra subpopulation and the efficacy for pioglitazone within high-risk non-Caucasian subjects.

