The sample size for this study is based on the event-driven analysis that is planned for comparing treatment groups within the high-risk stratum. For the purposes of this study, it is assumed that the placebo-treated non-Hispanic/Latino Caucasian subjects in the high-risk stratum will have an event rate of 15% over a 5-year period. This is more conservative than the 18% cited in the table, to assure adequate sample size. With an expected improvement of a reduction in event rate of 40%, the target event rate for the active treatment group will be 9% over 5 years. Furthermore, the following specifications are used: alpha=0.01, a 2-sided statistical test based on survival analysis, power=90%, annual dropout rate of 12% (or cumulative dropout rate of 47% over 5 years). In order to detect a difference of the specified magnitude ($\geq 40\%$ reduction in conversion rates over 5 years), at least 202 events must be observed during the course of the study in non-

Hispanic/Latino Caucasian subjects (primary analysis). Based on these assumptions and the fact that only non-Hispanic/Latino Caucasian subjects will be used for the primary analyses, a total of 2,346 non-Hispanic/Latino Caucasian subjects (1,173 on pioglitazone/1,173 on placebo) are required from the high-risk stratum for randomization.

Sample Size for the Phase 3 Study Based On Qualifying the Test Used to Stratify Subjects

While using data from the results of risk stratification and not a comparison between randomized groups, the same analysis as specified for comparing the treatment groups within the high-risk stratum will also be used to compare the two placebo groups (high-risk placebo and low-risk placebo). Thus, assuming that the placebo-treated subjects in the low-risk stratum will have a conversion rate of 4% over a 5-year follow-up period, then approximately 314 non-Hispanic/Latino Caucasian subjects identified as low-risk for the event are required in that stratum. While this number of subjects enrolled in the low-risk stratum will provide very high power (99% with $\alpha=0.01$) to validate the enrichment algorithm with the assumed 5-year conversion rates (ie, 15% vs. 4%).

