9.1.4 Grouping of Centers

Pooling of small sites will be done (if necessary) to form centers for purposes of analysis.

Before unblinding the study, sites that are considered small (<40 subjects) will be pooled with geographically similar sites to minimize artifacts in the statistical analyses from imbalances in subject counts within the sites.

Starting with the smallest center, center(s) with fewer than 40 subjects randomized will be pooled into the nearest center. The pooling will start first within each country; if it is still small, other countries within the same geographical region (for example, US, Europe, Rest of World) will also be considered. The pooled centers within a region which still have fewer than 40 subjects will be kept as they are and will not be pooled with centers in other regions.

The pooling of the centers will be reviewed and approved by the clinical and statistical team for agreement, and will then be used in the appropriate analyses once the database has been locked and unblinded.

Quality issues were detected at site 5055; therefore, data collected exclusively at that site will be excluded for purposes of efficacy analyses.

Because of the smaller number of events available at the time of the efficacy futility analysis, pooling will be done for the efficacy futility analysis using a smaller number of pooled centers, based on country/sovereign state, as shown below.

- US
- UK
- Australia
- Switzerland/Germany

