9.9.3.5 Supportive PPS and subgroup analyses

If more than 5% of total subjects in the FAS high-risk, non-Hispanic/Latino Caucasian subjects have major protocol violations, the primary efficacy analysis will also be performed based on the PPS.

Similarly, if more than 5% of total subjects in the FAS placebo (both high-risk and low-risk), non-Hispanic/Latino Caucasian subjects have major protocol violations, the primary biomarker analysis will also be performed based on the PPS.

For the primary efficacy variable (for both the primary efficacy comparison and for the primary biomarker comparison), subgroup analyses by:

- age at randomization (<75, ≥75)
- gender (female, male)
- baseline diabetic status (non-diabetic: baseline HbA1c <6.5%, diabetic: baseline HbA1c ≥6.5%)
- race/ethnicity (Hispanic/Latino and/or non-Caucasian, all subjects)
- baseline NPI-Q Apathy/Indifference Score (no symptoms; mild, moderate, or severe symptoms)
- regulatory geographic region (North America: US; Europe: UK, Germany, Switzerland; Rest of World: Australia)
- geographic region based on language (English, German)
- baseline statin use (based on the Standardized Drug Groupings maintained by Uppsala Monitoring Centre, sponsors of the WHO Drug dictionaries)

and other variables, if necessary, will be performed. Analysis results for subgroups containing less than 20% of the total subjects in the primary efficacy analysis population should be interpreted especially cautiously. The treatment groups will be compared within each subgroup.

CCI

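### With no events among the roughly 20 low-risk Hispanic/Latino and/or non-Caucasian subjects, the robust-sandwich Cox test of the biomarker rejects almost automatically

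*SAP*

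**What the plan says.** SAP 9.9.3.1 tests the biomarker with a Cox model adjusted for center, gender and education, at the 0.01 level and with 99% CIs. On the variance it says: "The robust sandwich estimate for the covariance matrix from the CPH model will be used". SAP 9.9.3.2 repeats this for efficacy and adds age.

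Two places carry the analysis into the small group. SAP 9.9: "All primary and key secondary efficacy analyses and summaries will be presented separately for the following groups of subjects", and the list that follows includes Hispanic/Latino and/or non-Caucasian subjects. Protocol 13.1.3: "These analyses will be the same as those conducted for the primary subgroup of the Caucasian subjects", with evaluation of the biomarker in that population as a stated purpose. Protocol 6.1 and SAP 6.4 put the group at 167 subjects.

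SAP 9.9.3.5 extends the comparisons further: "For the primary efficacy variable (for both the primary efficacy comparison and for the primary biomarker comparison), subgroup analyses by" age, gender, diabetic status, race/ethnicity and other factors.

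For the final analysis, neither document says what to do when a compared group has no events or very few. SAP 9.1.4 does coarsen center to country groups for the futility look, "Because of the smaller number of events available at the time of the efficacy futility analysis". SAP 9.16 requires a subgroup to hold at least 20% of the events before it is analyzed at that look. Neither rule is applied to the final analyses.

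**The concern.** The robust variance behaves badly when one group has no events. Suppose all events are in the high-risk group. As the low-risk log hazard ratio b runs to minus infinity, the information shrinks in proportion to exp(b). Every score residual also shrinks in proportion to exp(b), so their sum of squares shrinks as exp(2b). The sandwich variance is that sum divided by the information squared, so the factors cancel and the robust SE settles at a finite value. The model-based SE grows without limit instead.

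The Wald ratio is therefore a very large number over a moderate one. A sample with no events among about 20 people, which carries almost no information, is printed with a minute p-value and a very narrow interval. The study report could then appear to confirm a genetic risk algorithm in the populations in which it was not developed.

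**Working it through.** **Inputs from the documents.** Five-year rates of 15% (high-risk placebo), 4% (low-risk) and 9% (active); 12% annual dropout; exponential event times; two-sided alpha 0.01; 202 target events; 314 low-risk subjects required; 2,940 high-risk and 394 low-risk expected; 167 in the small group; study end about four years after enrollment closes (Protocol 9.3.6); about 20% diabetic (Protocol 13.1.3).

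**Assumptions.** The 167 split like the main population: 167 × 394/3,334 ≈ 20 low-risk, and 167 × 2,940/3,334 ÷ 2 ≈ 73–74 high-risk placebo. Follow-up was varied from 3.5 to 5.5 years. The p-value and CI are taken to be Wald type because they rest on the robust covariance matrix; SAP 9.16.1 names the Wald statistic for the futility look.

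**The plan's own figures.**
- Efficacy: HR = ln 0.91/ln 0.85 = 0.580. Events = 4 × (2.576 + 1.282)²/(ln 0.580)² ≈ 201, against 202 stated.
- Biomarker: HR = ln 0.96/ln 0.85 = 0.251. At 4 years, 1,173 vs 314 subjects give about 112.6 + 7.9 = 120.5 events. With low-risk share 314/1,487 = 0.211, power = Φ(1.382 × √(120.5 × 0.211 × 0.789) − 2.576) > 0.999. The plan states 99%.

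**Chance of no low-risk events.** With λ = −ln(1 − rate)/5 and δ = −ln 0.88 = 0.128, the probability of an observed event by time T is p = λ/(λ+δ) × (1 − exp(−(λ+δ)T)). For 20 subjects, P(zero) = (1 − p)²⁰.

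| Low-risk rate | T = 4 years | T = 5.5 years |
|---|---|---|
| 4% (as planned) | p = 0.0252, P(zero) = 60% | p = 0.0316, P(zero) = 53% |
| 15% (no difference) | p = 0.0960, P(zero) = 13% | p = 0.1188, P(zero) = 8% |

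At 3.5 years the formula gives 63% and 16%. Simulations with shorter follow-up gave 62% and 18%. At 4 years the group expects about 20 × 0.0252 = 0.5 low-risk events and 73 × 0.0960 = 7 high-risk placebo events.

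**What the test does then.** In simulated samples with zero low-risk events, the estimate stopped between about −16 and −20, depending on the convergence rule. The robust SE was about 0.4–0.75 and the model-based SE was in the thousands. For example, −16.4 with robust SE 0.47 gives |z| = 16.4/0.47 ≈ 35, and a 99% CI of exp(−16.4 ± 2.576 × 0.47), about 2×10⁻⁸ to 3×10⁻⁷. Rejection was 100% without covariates and 98–100% with covariates.

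**False-positive rate at nominal 1%, 20 vs 73 subjects.**

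| Common 5-year rate | Robust test |
|---|---|
| 15% | 10–11% (follow-up spread over 4–5.5 years), 14% (4 years), 18% (3.5 years) |
| 9% | 24–35% |
| 4% | 54–59% |

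The likelihood-ratio test gave 0.3–1.3% in the same group. At the planned 15% vs 4%, the robust 99% CI missed the true hazard ratio in 59–64% of trials.

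**A 20% subgroup such as diabetics** (0.2 × 394 ≈ 79 low-risk, 0.2 × 1,470 = 294 high-risk placebo). At a common 15% rate the false-positive rate was 0.7–1.1%. At the planned 15% vs 4%, the 99% CI missed the true value in about 12–19%, and power was about 12–18% robust vs 36–47% likelihood ratio.

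**Primary tests.** For the required 314 low-risk subjects at 4 years, P(zero) = (1 − 0.0252)³¹⁴ ≈ 0.03%. Simulated false-positive rates for the primary biomarker test were 0.7–1.6%, compatible with 1%. The primary efficacy test gave 1.1%.

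**The case against.** The strongest reply is that the documents already limit reliance on these results. Protocol 6.1 calls the data in this group limited and exploratory. SAP 9.9.3.5 asks for special caution below a 20% share. SAP 9.9.8 leaves the analyses out of the testing sequence. The decision rule in SAP 9.9.3.1, "If this test is significant at the 0.01 level, it can be concluded that the diagnostic prognostic test has differentiated", belongs to the non-Hispanic/Latino Caucasian comparison. SAP 9.9.3.3 permits other methods if model assumptions fail, and SAP 9.9.3.4 adds a log-rank test. A careful reader would also recognize a hazard ratio near exp(−16) as non-estimable. All this lowers the stakes. It does not correct the p-value and CI that the SAP tells the programmer to report, and the switch of method is discretionary.

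Stronger readings are tempting, and the documents do not support them:

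- *A fixed false-positive rate of 17–34%.* At the 15% rate with follow-up of at least four years it is about 10–14%. Higher values need shorter follow-up, a lower common rate or an assumed 20–45 pooled centers, and no document gives the number of centers.
- *Zero low-risk events are likely when there is no true difference.* They are likely at the 4% rate, where the groups really differ and a rejection is not a false positive. Under a common 15% rate they are a minority outcome.
- *All subgroups give false positives.* The diabetic subgroup does not at a common 15% rate, and reaches only 1.7% at 9%. It rises to 10.5% at a common 4%.
- *Efficacy in the 167 is distorted too.* Without center terms its false-positive rate was 0.5%; inflation appeared only with the assumed center counts.

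**Conclusion.** The point holds for the biomarker comparison in the Hispanic/Latino and/or non-Caucasian group. A prescribed test gives a wrong p-value and CI in a foreseeable case. At nominal 1% its false-positive rate is about 10–18% if both risk groups have a 15% five-year rate, depending on follow-up. It is about 24–35% at a common 9% and 54–59% at a common 4%. These figures rest on the assumed split giving about 20 low-risk subjects and on the plan's dropout rate and exponential model.

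In a subgroup of about 20% the defect is poor CI coverage and lost power at the planned rates; false-positive inflation at a common 15% rate is negligible. A reader might infer that the primary biomarker or efficacy conclusion is at risk. It is not: both tests keep their level and zero low-risk events there are very improbable. This is a defect in supportive analyses, worth correcting before unblinding.

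**What to change.** In SAP 9.9 and 9.9.3.5, add a rule for the Hispanic/Latino and/or non-Caucasian analyses and for any subgroup comparison in which a compared group has zero or very few events:

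- Replace the robust Wald p-value and CI with a likelihood-ratio test and a profile-likelihood 99% CI, giving a one-sided bound when a group has no events.
- Omit center, or use the country groups of SAP 9.1.4.
- Show event counts and person-years by group.

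The SAP should state the number that counts as very few before unblinding; the documents give no basis for a particular value. Leave the two primary analyses and the well-populated subgroups unchanged.

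The cost is SAP wording and a few program options, with no new data. The small downside is a wide or one-sided interval in the smallest groups, which reflects what those data can show.
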